### **5.2.5. Definition of start of new anti-cancer drug therapy**

Start date of new anti-cancer drug therapy is used to determine the end of the on-treatment period (see [Section 5.2.7](#)).

The start date of new anti-cancer drug therapy is the earliest start date of anti-cancer drug therapy recorded in the ‘Follow-up Cancer Therapy’ eCRF pages that is after the first dose of study treatment. When start date of anti-cancer drug therapy is missing or partially missing, the imputation rules described in [Section 5.3.3.4](#) should be applied using only data from the ‘Follow-up Cancer Therapy’ eCRF pages.

### **5.2.6. Definition of start of new anti-cancer therapy**

Start date of new anti-cancer therapy (drug, radiation, surgery) is used for censoring in sensitivity analyses for the primary efficacy endpoint of EFS for Arm A vs Arm C and the key secondary endpoint of EFS for Arm B vs Arm C (see [Section 6.2.2.3](#)).

The start date of new anti-cancer therapy is the earliest date after ‘start date’ amongst the following:

- Start date of anti-cancer drug therapy recorded in the ‘Follow-up Cancer Therapy’ eCRF pages
- Start date of radiation therapy recorded in ‘Follow-up Radiation Treatment’ eCRF pages.
- Surgery date, for lesions with a positive biopsy other than low grade Ta, or lesions with missing biopsy results, per the ‘Oncology Biopsy’ eCRF page, recorded in ‘On Study & Follow-up Cancer Surgery’ eCRF pages when ‘Outcome of Procedure’ = ‘Resected’ or ‘Partially Resected’.

When start date of anti-cancer therapy is missing or partially missing, the imputation rules described in [Section 5.3.3.4](#) should be applied using ‘Follow-up Cancer Therapy’, ‘Follow-up Radiation Treatment’, and ‘On Study & Follow-up Cancer Surgery’ eCRF pages.

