4.1.1. BCG-Naïve Cohort (Cohort A)

A total of approximately 999 participants with BCG naïve, high-risk, NMIBC (including a minimum of 250 participants with CIS) will be randomized in a 1:1:1 ratio to one of 3 treatment arms below. As of 16 November 2021, enrollment to Cohort A has completed with 1056 participants randomized.

- Arm A: PF-06801591 + BCG (induction and maintenance period)
- Arm B: PF-06801591 + BCG (induction period only)
- Arm C: BCG only (induction and maintenance period)

BCG Dosing:

- Induction period: one dose every week via intravesical instillation for 6 consecutive weeks (QWx6: Cycle [C]1Day [D]1, C1D8, C1D15, C1D22, C2D1, C2D8)
- Re-Induction period: Following first induction period, participants with CIS at randomization who have persistent disease and participants with recurrence of high- grade Ta disease may receive re-induction with one dose every week via intravesical instillation for up to 6 consecutive weeks. Suggested schedule is C4D1, C4D8, C4D15, C4D22, C5D1, C5D8. Maintenance will then begin on C7D1. If TURBT is performed, schedule for BCG re-induction should be modified according to the product label.
- Maintenance period: (Arm A and Arm C): Doses on D1, D8, D15 during Cycles C4, C7, C13, C19 and C25. For participants that have a re-induction period, the maintenance period will begin at C7D1.

PF-06801591 Dosing

Once every 4 weeks (Q4W) 300 mg SC up to Cycle 25.

Randomization will be stratified by the presence of CIS (yes vs no) and geography (US vs Western Europe and Canada vs ROW).

The study was initially designed with two primary objectives: 1) to demonstrate that PF-06801591 given in combination with BCG (induction and maintenance) is superior to BCG alone (induction and maintenance) in prolonging EFS in participants with high-risk NMIBC and 2) to demonstrate that PF-06801591 given in combination with BCG (induction only) is superior to BCG alone (induction and maintenance) in prolonging EFS in participants with high-risk NMIBC.

The study was initially designed with two key secondary objectives: 1) to demonstrate that PF-06801591 + BCG (induction and maintenance) is superior to BCG (induction and maintenance) in prolonging OS in participants with high-risk NMIBC and 2) to demonstrate that PF-06801591 + BCG (induction) is superior to BCG (induction and maintenance) in prolonging OS in participants with high-risk NMIBC.

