6.5.7. Surgery

Caution is advised on theoretical grounds for any surgical procedures during the study. The appropriate interval of time between surgery and PF-06801591 required to minimize the risk of impaired wound healing and bleeding has not been determined. Stopping PF-06801591 is recommended at least 7 days prior to surgery. Postoperatively, the decision to reinitiate PF-06801591 treatment should be based on a clinical assessment of satisfactory wound healing and recovery from surgery. TURBT is allowed during the study conduct in case of positive cystoscopy (presence of malignant or suspicious lesions) and it will be performed as indicated by local guidance. BCG administration should be modified according to the product label after TURBT. See also 10.9 for disease assessment guidance.

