### 2.2.1. Primary estimand (Cohort A only)

Primary Estimand (EFS for Arm A vs Arm C): treatment effect, estimated based on data from all randomized participants, of Arm A on EFS compared to Arm C from randomization to the earliest of recurrence of high-grade disease, progression of disease, persistence of CIS, or death regardless of tolerability, duration of study treatment, or initiation of subsequent anti-cancer therapy. The date of the event (event as defined in Table 10) is the date of disease assessment documenting recurrence of high-grade disease, progression of disease, persistence of CIS (applicable only to participants with CIS at randomization), or death, whichever occurs earlier. The date of persistence of CIS is the earliest date when persistence of CIS is observed, if CR is not observed after re-induction.

- Variable: EFS defined as the time from randomization until recurrence of high-grade disease, progression of disease, persistence of CIS or death due to any cause, whichever occurs first.
- Censoring: see Table 11.
- Population-level summary measure: hazard ratio for EFS including all randomized participants.

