### **Definition of baseline:**

‘Start date’ will be defined as date of randomization for Cohort A and date of first dose for Cohorts B1 and B2.

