#### 6.2.2.3. Sensitivity analyses for event-free survival (Cohort A only)

The following analyses will be performed to explore the robustness of the primary analysis results. The sensitivity analyses will repeat the primary analysis (p-value, HR and 95% CIs) described in [Section 6.1.1.1](#) with the modifications below:

- EFS based on BICR results following the definitions in Table 10 and the censoring rules outlined in Table 11 and Table 12.
- EFS based on investigator assessment where the date of the event for participants with persistence of CIS is the date of randomization (refer to Supportive Estimand 1 [Section 2.2.3](#))
- EFS based on investigator assessment following the definitions in Table 10 and the censoring rules outlined in Table 11 and Table 12 for participants in the per-protocol analysis set (refer to Supportive Estimand 2 [Section 2.2.3](#))
- EFS based on investigator assessment following the definitions in Table 10 and the censoring rules outlined in Table 11 and Table 12 and using an unstratified analysis.
- EFS based on investigator assessment following the definitions in Table 10 and modifying the censoring rules in Table 11 (update footnote “a” to “If the participant dies  $\leq 24$  weeks after the date of randomization and did not initiate new anti-cancer therapy, the death is an event with date on death date”) and Table 12 to include initiation of subsequent anti-cancer therapies as a censoring reason after “no adequate baseline assessment”.
- EFS based on investigator assessment following the definitions in Table 10 and the censoring rules outlined in Table 11 and Table 12 and using CIS stratification factor derived based on the data entered by the investigator in the “Oncology Biopsy” eCRF at Screening.
- EFS based on investigator assessment following the definitions in Table 10 and modifying the censoring rules in Table 11 and Table 12 to not censor events after 2 or more missing or inadequate post-baseline disease assessments (ie. all events will be counted).
- If  $>10\%$  of deaths are due to COVID-19, an analysis will be performed for EFS (primary definition excluding COVID-19 related deaths) by treating COVID-19 related deaths as a competing risk event.
- If there are  $>10\%$  of participants with missed visits resulting in 2 or more missing assessments or inadequate post-baseline disease assessments due to COVID-19 before EFS events, censoring for event after 2 or more missing or inadequate disease assessment

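### In one EFS sensitivity analysis, a TURBT permitted before BCG re-induction counts as new anti-cancer therapy, so censoring depends on the later response to study treatment

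*SAP*

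**What the plan says.** SAP 5.2.6 gives the variable its purpose: "Start date of new anti-cancer therapy (drug, radiation, surgery) is used for censoring in sensitivity analyses for the primary efficacy endpoint of EFS". Both experimental-arm comparisons are covered. The date is the earliest after randomization among anti-cancer drug, radiation and surgery. The surgery item reads "Surgery date, for lesions with a positive biopsy other than low grade Ta, or lesions with missing biopsy results". It draws on the page that records on-study as well as follow-up surgery, and the outcome must be full or partial resection. The only exempted malignant finding is low-grade Ta.

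SAP 6.2.2.3 changes the censoring hierarchy "to include initiation of subsequent anti-cancer therapies as a censoring reason after" the missing-baseline reason. It gives neither the censoring date nor the order in which event and therapy are compared.

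Protocol 6.5.7 allows TURBT on study after a positive cystoscopy. For re-induction, Protocol 4.1.1 adds: "If TURBT is performed, schedule for BCG re-induction should be modified according to the product label". The suggested re-induction starts at C4D1, which is week 12.

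For the event, SAP 2.2.1 states: "The date of persistence of CIS is the earliest date when persistence of CIS is observed, if CR is not observed after re-induction". Footnote b of SAP Table 10 says that persistence followed by CR after re-induction is not an event. SAP 5.2.12 dates persistence at the earliest positive biopsy, cystoscopy or cytology.

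**The concern.** The primary estimand ignores new therapy. This is the only listed EFS sensitivity analysis that asks what happens when follow-up after subsequent therapy is set aside. To answer that, it should remove follow-up affected by therapy outside the randomized regimen. As written, it can also remove participants who are still receiving their randomized regimen, and it selects them by whether re-induction worked.

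Table 10 has two relevant non-events: low-grade Ta recurrence, and CIS persistence rescued by re-induction. SAP 5.2.6 exempts surgery for the first but not for the second. If rescue differs between arms, the loss of later follow-up differs too. A gap between this analysis and the primary one could then be put down to subsequent therapy when it comes from the definition.

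**Working it through.** **1. The plan's own figure.** The documents give no figure for this sensitivity analysis. The primary power (SAP 5.1.1) reproduces: z = (√174 / 2) × |ln 0.69| − 1.960 = 6.595 × 0.371 − 1.960 = 0.487, and Φ(0.487) = 68.7%, as stated. Nothing below changes it.

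**2. Date trace.** Take two participants with CIS at randomization, the same week-12 finding, the same resection of biopsy-positive CIS, and re-induction. The usual convention is assumed: events on or before new therapy count, otherwise censor at new therapy.

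| | CR after re-induction | No CR after re-induction |
|---|---|---|
| Week-12 persistence | not an event (Table 10, footnote b) | event (SAP 2.2.1) |
| Event date | none yet | earliest positive week-12 result, so on or before the TURBT (SAP 5.2.12) |
| TURBT under SAP 5.2.6 | new therapy | new therapy |
| Sensitivity analysis | censored at about week 12, later events lost | event at about week 12 |

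Only the later result of study treatment separates the columns. High-grade Ta recurrence at week 12 does not behave this way, because Table 10 makes it an event whatever re-induction shows.

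**3. Number affected.** The planned minimum is 250 CIS participants in three arms, 250/3 = 83.3 per arm. Expected number censored = 83.3 × P(persistent) × P(qualifying TURBT) × P(rescued). All three rates are assumptions:

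- 20%, 25%, 30%: 1.2 per arm
- 35%, 50%, 50%: 7.3 per arm
- 50%, 100%, 70%: 29.2 per arm

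**4. HR in the CIS stratum (illustration).** Assumed: 35% persistent in each arm, control median 24 months after week 12, HR 0.69 after week 12, follow-up to 36 months, 200,000 simulated per arm. The last column puts the censoring just after / just before the failures' event date.

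| Rescue A / C | TURBT share | Later hazard if rescued | HR without rule | HR with rule |
|---|---|---|---|---|
| 50% / 50% | 50% | 2x | 0.766 | 0.772 / 0.772 |
| 50% / 50% | 100% | 2x | 0.765 | 0.779 / 0.785 |
| 70% / 30% | 50% | 1x | 0.607 | 0.599 / 0.620 |
| 70% / 30% | 50% | 2x | 0.668 | 0.639 / 0.646 |
| 70% / 30% | 100% | 2x | 0.667 | 0.599 / 0.629 |
| 70% / 30% | 100% | 3x | 0.702 | 0.601 / 0.628 |

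Differences below about 0.01 are within simulation noise.

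**5. Whole-trial HR (illustration).** Assumed: CIS share 25% (250/999), 352 per arm (1056/3), stratified Cox model. CIS control hazard is 0.0045/month (x0.8 experimental), non-CIS control hazard 0.006 to 0.009/month with HR 0.69, and follow-up 36 to 58 months.

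- 30% persistent, 50% TURBT, rescue 70% vs 50%, 2x: 2.6 vs 2.2 events lost per arm; HR 0.704 to 0.699, or 0.707 to 0.701.
- 35%, 25%, 70% vs 50%, 2x: shift 0.003 to 0.004.
- 35%, 50%, 70% vs 50%, 1x: shift 0.002 to 0.003.
- 40%, 80%, 70% vs 40%, 4x (extreme): shift 0.024 to 0.030; 9% to 12% of Arm A events lost.

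Equal rescue gives essentially no shift. For scale, the standard error of log HR at 174 events is about 2/√174 = 0.15.

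**6. The unstated order matters too.** If rescued participants were censored before the failures' event date, the week-12 event-free rate would also be biased. With 35% persistent, all with TURBT and 50% rescued, the true rate is 1 − 0.35 × 0.5 = 0.825. With rescued participants out of the risk set it is 1 − 0.175/0.825 = 0.788.

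**The case against.** The other side has real weight. This is one item in a list of EFS sensitivity variations and carries no alpha. The low-grade Ta exemption looks deliberate, and treating resection of high-grade tumour as anti-cancer intervention is defensible. The trigger is narrow: TURBT is optional and tied to a positive cystoscopy, persistence can also rest on cytology plus biopsy, and a diagnostic biopsy without resection does not count. The trace also relies on a censoring convention that SAP 6.2.2.3 does not write down.

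Most of this stands, and it sets the severity. It does not remove the defect. SAP 6.2.2.3 calls the censoring reason subsequent therapy, and Protocol 8.2.6 documents such therapy for participants who have discontinued study intervention. An on-study TURBT within the re-induction pathway fits neither description. And however resection is classed, censoring should not hinge on a response observed afterwards.

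Three stronger readings are tempting and not supported:

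- **The EFS result itself is biased.** The primary and key secondary EFS estimands disregard new therapy, so SAP 5.2.6 does not enter them.
- **The analysis is tilted toward the experimental arms.** That needs better rescue there and, in these illustrations, a worse later hazard in rescued participants. The documents state neither. With equal rescue the CIS-stratum HR moves slightly toward 1, and with unequal rescue but equal later hazard it can move either way (0.607 to 0.599 or 0.620).
- **A large share of an arm's events disappears.** Shares near 30% arise only within the CIS stratum at extreme assumptions. In the moderate whole-trial case the loss is 2% to 4% of an arm's events.

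**Conclusion.** The point holds and is minor. The SAP 5.2.6 surgery item has no exemption for TURBT before BCG re-induction. On the usual reading, whether a CIS participant with week-12 persistence and a qualifying TURBT is censored or counted then depends on the later re-induction result.

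Only the sensitivity analysis that censors at subsequent therapy is affected. Its size cannot be derived from the documents, which give no persistence, TURBT or rescue rates. Under the assumptions shown, the CIS-stratum HR moves little when rescue is equal. It moves by roughly 0.02 to 0.09 toward the experimental arm (0.10 in the last row of the table) when rescue is better there and rescued participants fare worse later. The whole-trial shift is about 0.00 to 0.02, up to 0.03 at the extreme. The direction is not established.

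The conclusion also assumes that events on or before new therapy count. That convention is missing from SAP 6.2.2.3 and should be written in any case.

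**What to change.** In SAP 5.2.6, do one of two things. Limit the surgery item to cystectomy and to surgery after discontinuation of all study treatment, or exempt a TURBT done before or as part of protocol BCG re-induction. Do not define the exemption by whether study treatment later continued. CIS participants without CR within 6 months are withdrawn from treatment (Protocol 7.1), so that wording would again condition on response.

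In SAP 6.2.2.3, state the censoring date (the last adequate disease assessment before new therapy) and that events on or before new therapy count. Say also whether a week-12 persistence later rescued is an assessment documenting no event. If it is not, the censoring date could fall back to randomization.

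Optionally, show on-study TURBT on its own line in the descriptive table of SAP 6.5.5, which draws on the same surgery page.

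The cost is a few sentences plus programming against dosing dates already collected. The downside is that a TURBT that in practice replaced study treatment is no longer a censoring point unless treatment stopped.

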### **5.2.7. Definition of on-treatment period**

Safety endpoints will be summarized based on the on-treatment period unless otherwise specified.

On-treatment period is defined as the time from the first dose of study treatment through minimum (30 days + last dose of study treatment, start day of new anti-cancer drug therapy – 1 day) (also refer to Appendix 1 for irAEs).

Safety data collected outside the on-treatment period as described above will be listed and flagged in listings but will not be summarized.

### **5.2.8. Standard derivations and reporting conventions**

The following conversion factors will be used to convert days into weeks, months or years: 1 week = 7 days, 1 month = 30.4375 days, 1 year = 365.25 days.

Age [years]: (year of given informed consent – year of birth)

For reporting conventions, mean and median should generally be displayed one more decimal place than the raw data and standard deviation should be displayed to two more decimal places than the raw data. Percentages will be reported to one decimal place. The

rounding will be performed to closest integer / first decimal using the common mid-point between the two consecutive values. E.g., 5.1 to 5.4 will be rounded to an integer of 5, and 5.5 to 5.9 will be rounded to an integer of 6.

### **5.2.9. Unscheduled visits**

Generally, data collected at unscheduled visits will be included and analyzed for both safety and efficacy analyses in the same fashion as the data collected at scheduled visits except where otherwise noted in the sections that follow. Descriptive statistics (mean, SD, median, minimum, maximum, quartiles) by nominal visit or time point for safety endpoints such as laboratory measurements, electrocardiograms (ECGs) and vital signs will include only data from scheduled visits

### **5.2.10. Adequate baseline disease assessment**

Adequate baseline is defined using the following criteria:

#### Cohort A, for the analysis of EFS per Investigator and per BICR

- All participants with CIS at baseline by the investigator are deemed to have adequate baseline disease.
- Participants without CIS at baseline by the investigator are deemed to have adequate baseline disease if all of the following criteria are met:
  - Baseline cystoscopy performed within 35 days prior to and including the date of randomization.
  - Baseline assessment for cystoscopy as collected on the “Cystoscopy” eCRF page must indicate “Yes” for “was Cystoscopy performed” and the cystoscopy result is “Negative”.
  - Baseline cytology as collected on the “Lab Urine Cytology” eCRF page is not “Positive”.

#### Cohort B1

- All participants with CIS by BICR at baseline are deemed to have adequate baseline disease.

#### Cohort B2

- Participants without CIS at baseline by the investigator are deemed to have adequate baseline disease if all of the following criteria are met:
  - Baseline cystoscopy performed within 35 days prior to and including the date of registration.

- Baseline assessment for cystoscopy as collected on the “Cystoscopy” eCRF page must indicate “Yes” for “was Cystoscopy performed” and the cystoscopy result is “Negative”.
- Baseline cytology as collected on the “Lab Urine Cytology” eCRF page is not “Positive”.

### **5.2.11. Adequate post-baseline disease assessment**

An adequate post-baseline disease assessment is defined as an assessment recorded with progression of disease (all participants), recurrence of high-grade disease (all participants), recurrence of low-grade disease (participants without CIS at randomization (Cohort A/Cohort B2), CR (participants with CIS at randomization (Cohort A)/baseline (Cohort B1)), persistence of CIS disease (participants with CIS at randomization (Cohort A)/baseline (Cohort B1), or no evidence of disease (participants without CIS at randomization (Cohort A)/baseline (Cohort B2)) (Section 5.2.12). Time points where the response is not evaluable (NE) or no assessment was performed will not be used for determining the censoring date.

